6.2 Subject demographics/other baseline characteristics

All baseline assessments should be performed prior to the first study treatment administration.

6.2.1 Demographics

Subject demographic data to be collected on all subjects include: date of birth, subject initials, sex, race, ethnicity and child-bearing potential (for females only).

6.2.2 Psoriasis history / Prior psoriasis therapies

Disease history will be collected at the screening visit. The information to be collected and entered in the eCRF includes the following:

- date of first diagnosis of plaque psoriasis (by a physician);
- previous psoriasis treatments (including previous use of systemic therapies, as well as phototherapy and/or photochemotherapy), duration of exposure, and the reason for discontinuation of each therapy;
- presence of psoriatic arthritis and the date of first diagnosis (by a physician).

6.2.3 Smoking history

The current and/or previous use of tobacco products will be recorded, as well as the estimated number of pack-years based on the approximate consumption per year. Non-smokers will be advised to not start smoking during the study.

6.2.4 Alcohol use history

The current and/or previous use of alcohol will be recorded. This includes the estimated number of alcoholic drinks consumed on average per day, and the date alcohol was last consumed. Current alcohol use will be assessed throughout the duration of the study at the scheduled visits as indicated in [Table 6-1](#).

6.2.5 Comorbidities – cardiovascular history

Any information pertaining to cardiovascular medical history assessed prior to randomization should be reported on the Cardiovascular History eCRF.

Additionally, family history of certain cardiovascular diseases will also be collected.

6.2.6 Relevant medical history / Current medical conditions

Relevant medical history/current medical conditions, not including psoriasis or psoriatic arthritis, will be recorded on the Medical History eCRF.

Relevant medical history/current medical conditions will include data up to six months prior to signing of the informed consent. Whenever possible, diagnoses (and not symptoms) will be recorded.

Significant findings that are observed after the subject has provided informed consent, and that meet the definition of an AE, must be recorded on the Adverse Event eCRF.

Investigators will have the discretion to record abnormal test findings on the Medical History eCRF when in their judgment, the test abnormality occurred prior to the informed consent signature.

6.2.7 Prior and concomitant medications

Concomitant medications and prior medications taken over the six months preceding study enrollment will be captured at the Screening visit, and updated at Visit 2/Baseline.

6.2.8 Determination of tuberculosis status

Determination of tuberculosis (TB) status will be required before administration of study treatment. TB status must be determined by medical history, signs, symptoms, and TB testing (QuantiFERON-TB Gold assay). Any significant findings will be recorded in the appropriate eCRF(s), as necessary.

If the QuantiFERON-TB Gold Assay test is positive or indeterminate, a TB workup should be performed as defined by local guidelines to determine the subject's TB status.

QuantiFERON TB-Gold In-Tube assay

A QuantiFERON® TB-Gold In-Tube assay will be performed to assess the TB status at screening for all subjects. This test will only be used to determine subject's eligibility for the trial. The test will be used to screen the subject population for latent tuberculosis infection (Doherty, Van Vorhees and Lebwohl | 2008).

This blood-based assay is specific for Mycobacterium tuberculosis and is not influenced by previous Bacillus Calmette-Guérin vaccination or exposure to other Mycobacteria species.

This test, in contrast to the purified protein derivative (PPD) skin test, is also insensitive to a booster effect since the subject is not exposed to the vaccine. The assay measures the production of interferon-gamma and presents it relative to a negative and a positive control sample (Manuel and Kumar 2008).

The QuantiFERON®-TB Gold assay test will be supplied by the central laboratory. Details on the collection, shipment of samples and reporting of results by the central laboratory are provided in the Laboratory Manual.

The results of a TB workup for a subject with a positive or indeterminate test must be recorded in the eCRF.

- If the test result is **negative**, the subject may be randomized
- If the test result is **positive**, the Investigator should perform a TB workup for the test result as per local procedures.
 - Subjects **positive** for latent TB per workup may be randomized to the trial if sufficient treatment has been initiated according to local routine clinical practice and will be maintained for the prescribed duration.
 - Subjects **positive** for active TB per workup are not eligible for the study.
 - Subjects **negative** for TB (no signs of latent or active TB) per workup may be randomized to the trial.
- If the test result is **indeterminate**, it is **recommended to repeat the test once**. The Investigator may decide to skip the repetition of the test and proceed directly to the workup (however this is not recommended). If a TB workup was conducted prior to screening, results from the workup can be used to assess eligibility if the workup was conducted within 12 weeks prior to randomization.
 - If the second test is negative, the subject may be randomized.
 - If the second test is positive or indeterminate, the Investigator should perform a TB workup as per local guidelines. The subject will not be eligible for randomization if: “active tuberculosis is present”, or if “latent tuberculosis is present” and is untreated as per local guidelines.

Refer to Section 13 (Appendix 2) to see a schematic of the tuberculosis screening process and subject eligibility with respect to TB testing.

6.2.9 Other baseline characteristics

Baseline characteristic data to be collected on all subjects include (all labs are central except where indicated) (see also [Table 6-1](#)):

- vital signs, hematology, clinical chemistry, viral serology (HIV, Hepatitis B and Hepatitis C), serum pregnancy, physical examination, height, weight; PASI, IGA mod 2011; DLQI.

6.3 Treatment exposure and compliance

All administered doses of secukinumab or placebo will be recorded on the Dosage Administration Record eCRF. Compliance will be assessed by Novartis and CRO study personnel using the Dosage Administration Record eCRF, medication numbers, Drug Label Form information, and information collected by IRT.

Subjects will be provided with a Self-Administration Log at Visit 8/Week 12 to record the date and time of all at-home study treatment administrations during the Double-blind Induction and Open-label Treatment Periods. Subjects will be instructed to return to the study site at each scheduled visit with their completed Self-Administration Log, where the dosing information will be transcribed by site staff into the Dosage Administration Record eCRF. Subjects will also be instructed to return all used/unused study treatment and packaging to the study site at each visit as part of the compliance check. At the final study visit (Visit 14/Week 52), the subject's Self-Administration Log will be retained in the subject's source documents.

The Investigator/qualified site staff should promote compliance by instructing subjects to attend the study visits as scheduled, to take the study treatments exactly as prescribed, and by reiterating that compliance is necessary for subject safety and the validity of the study. Additionally, sites will be instructed to contact subjects via telephone at the time of scheduled at-home dosing to check compliance and to ensure completion of the Self-Administration Log. Likewise, subjects should be instructed to contact the Investigator/qualified site staff if he/she is unable for any reason to attend a study visit as scheduled, or if he/she is unable for any reason to take the study treatment at home as prescribed.

6.4 Efficacy

The primary efficacy variable is the change from baseline in the target (arterial vascular uptake) to background (venous blood pool) ratio from the aorta. The primary analysis time point will be at Week 12.

The secondary efficacy variables are the following:

- Change from baseline in cardiometabolic biomarkers (cardiometabolic function [lipid particle size, HDL function (cholesterol efflux)], measures of inflammation [TNF-Alpha, IL-6, C-reactive protein, GlycA], adiposity [leptin and adiponectin], insulin resistance [insulin

levels/glucose to yield HOMA-IR], and markers predictive of diabetes [apolipoprotein B, ferritin, IL-2 receptor A, IL-18, and fetuin-A])

- PASI 75 response (yes, no)
- PASI 90 response (yes, no)
- PASI 100 response (yes, no)
- IGA mod 2011 score of 0 or 1 (yes, no)
- Change from baseline in DLQI total score

All efficacy assessments should be performed prior to the administration of study treatment and at all scheduled study visits as indicated in [Table 6-1](#).

Patient Reported Outcomes (PRO)

PROs should be collected prior to the Investigator performing any efficacy assessments:

- DLQI

Efficacy assessments (Investigator)

The following efficacy assessments performed by the Investigator will be completed for all subjects:

- PASI
- IGA mod 2011

6.4.1 Target (arterial vascular uptake) to background (venous blood pool) ratio from the aorta

Subjects will undergo vascular inflammation imaging assessments with full-body FDG-PET/CT scans at three scheduled visits – Visit 2/Baseline, Visit 8/Week 12 and Visit 14/Week 52 (see [Table 6-1](#)). The FDG-PET/CT scans will be conducted at each investigative site's local imaging center and the whole process should take approximately 3 hours to complete.

Subjects will be required to fast for a minimum of 8 hours prior to the imaging assessment. At the imaging center, the subject's glucose level will be checked by finger stick test and results should not exceed 150 mg/dL. If the glucose level exceeds 150 mg/dL, consultation with the Medical Monitor prior to the imaging will be required to determine if the subject is eligible to continue in the study. The whole-body PET/CT scan will be initiated approximately 120 minutes (\pm 10 minutes) after intravenous administration of [18F]-fluorodeoxyglucose (FDG).

Within approximately 24 hours after the completion of the FDG-PET/CT scan, the local nuclear medicine personnel will issue a clinical report determining if the subject has any clinically significant findings which would preclude the subject's continued participation in the study.

The arterial uptake of FDG will be measured by the standardized uptake value (SUV) max divided by the venous SUV mean ([Mehta et al 2012](#)). This will yield a target to background ratio

(TBR) which is considered the standard reporting variable in FDG-PET/CT vascular studies. The PET/CT images obtained from each site's local imaging center will be de-identified and should be sent to the [REDACTED] Imaging Lab within 1-3 days where trained nuclear medicine personnel will undertake a qualitative review of the PET/CT images. During this review, two-dimensional (2D) circular regions of interests (ROIs) will be manually placed on the PET images around the external aortic contour, around the hepatic margin, and around articular spaces on all transverse slices passing through these structures using low-dose CT images for anatomic guidance. The images will then be sent to the central core [REDACTED] Imaging Lab for measuring the SUVs. The [REDACTED] central PET/CT readers will be blinded to time and treatment via Digital Imaging and Communication in Medicine (DICOM) file editing applied by the [REDACTED].

The mean aortic SUV will be calculated for five segments of the aorta: ascending aorta, aortic arch, descending thoracic aorta, suprarenal abdominal aorta, and infrarenal abdominal aorta. These segments are defined to consider separately various regions of aortic disease that are associated with different clinical phenotypes (e.g., aortic arch disease with stroke, abdominal aortic disease with abdominal aortic aneurysm).

6.4.2 Cardiometabolic biomarkers

The following cardiometabolic biomarkers will be analyzed centrally at an analytical laboratory:

- Cardiometabolic function: lipid particle size, HDL function (cholesterol efflux);
- Inflammation: TNF-Alpha, IL-6, C-reactive protein, GlycA;
- Adiposity: leptin and adiponectin;
- Insulin resistance: insulin levels/glucose to yield HOMA-IR;
- Markers predictive of diabetes: apolipoprotein B, ferritin, IL-2 receptor A, IL-18, and fetuin-A.

Blood samples for cardiometabolic biomarkers will be collected at the scheduled time points as indicated in [Table 6-1](#).

Subjects will be required to fast for a minimum of 8 hours prior to the blood draw for the cardiometabolic biomarkers at the following visits only:

- Visit 2/Baseline
- Visit 8/Week 12
- Visit 14/Week 52.

A laboratory manual will be provided by the central laboratory with detailed information on biomarker sample collection, handling and shipment.

6.4.3 Assessment of total body surface area (BSA) and Psoriasis Area and Severity Index (PASI)

The Investigator or trained qualified designee will complete the PASI assessment at scheduled visits as indicated in [Table 6-1](#). Whenever possible, the same evaluator should perform this assessment at all study visits for a given subject. The Investigator is only responsible for collecting the components or scoring signs and total regional area. PASI calculations, including changes over time, will be done electronically, not by the Investigator.

The total BSA affected by plaque psoriasis will be estimated by the Investigator/trained qualified designee from the percentages of areas affected, including head, trunk, upper limbs and lower limbs (see below for full details of the PASI assessment). The following calculations will be done electronically: Each reported percentage will be multiplied by its respective body region corresponding factor (head=0.1, trunk=0.3, upper limbs=0.2, lower limbs=0.4). The resulting four percentages will be added up to estimate the total BSA affected by plaque psoriasis.

A PASI score ([Fredriksson and Pettersson 1978](#), [Weisman et al 2003](#), [Gottlieb et al 2005](#)) will be derived as indicated in [Table 6-3](#). The head, trunk, upper limbs and lower limbs are assessed separately by the Investigator/trained qualified designee for erythema, thickening (plaque elevation, induration), and scaling (desquamation). The average degree of severity of each sign in each of the four body regions is assigned a score of 0-4. The area covered by lesions on each body region is estimated as a percentage of the total area of that particular body region. The following practical details help the assessment:

1. The neck is assessed as part of the head
2. The axillae and groin are assessed as part of the trunk
3. The buttocks are assessed as part of the lower limbs
4. When scoring the severity of erythema, scales should not be removed.

Because the head and neck, upper limbs, trunk and lower limbs correspond to approximately 10%, 20%, 30% and 40% of the body surface area, respectively, the PASI score is calculated electronically within the eCRF using the following formula:

$$\text{PASI} = 0.1(E_H + I_H + D_H)A_H + 0.2(E_U + I_U + D_U)A_U + 0.3(E_T + I_T + D_T)A_T + 0.4(E_L + I_L + D_L)A_L$$

The keys for the letters are provided in [Table 6-2](#).

PASI scores can range from a lower value of 0, corresponding to no signs of psoriasis, up to a theoretic maximum of 72.0.

The baseline value for analysis of the PASI is collected at Visit 2/Baseline. A copy of the PASI is provided in Section 13 ([Appendix 3](#)).

Table 6-2 PASI scoring system

Body region	Erythema (E)	Thickening - plaque elevation, induration (I)	Scaling – desquamation (D)	Area score – based on true area % (A)*
Head (H) [†]	0=none	0=none	0=none	0=no involvement
	1=slight	1=slight	1=slight	1=>0-<10%
	2=moderate	2=moderate	2=moderate	2=10-<30%
	3=severe	3=severe	3=severe	3=30-<50%
	4=very severe	4=very severe	4=very severe	4=50-<70%
				5=70-<90% 6=90-100%
Trunk (T) [‡]	0=none	0=none	0=none	0=no involvement
	1=slight	1=slight	1=slight	1=>0-<10%
	2=moderate	2=moderate	2=moderate	2=10-<30%
	3=severe	3=severe	3=severe	3=30-<50%
	4=very severe	4=very severe	4=very severe	4=50-<70%
				5=70-<90% 6=90-100%
Upper limbs (U)	0=none	0=none	0=none	0=no involvement
	1=slight	1=slight	1=slight	1=>0-<10%
	2=moderate	2=moderate	2=moderate	2=10-<30%
	3=severe	3=severe	3=severe	3=30-<50%
	4=very severe	4=very severe	4=very severe	4=50-<70%
				5=70-<90% 6=90-100%
Lower limbs (L) [§]	0=none	0=none	0=none	0=no involvement
	1=slight	1=slight	1=slight	1=>0-<10%
	2=moderate	2=moderate	2=moderate	2=10-<30%
	3=severe	3=severe	3=severe	3=30-<50%
	4=very severe	4=very severe	4=very severe	4=50-<70%
				5=70-<90% 6=90-100%

*Percentage (not score) of body region (not whole body) affected will be entered in the eCRF

[†]Neck is assessed as part of the Head (H) body region

[‡]Axillae and groin are assessed as part of the Trunk (T) body region

[§]Buttocks are assessed as part of the Lower limbs (L) body region

Definitions of efficacy variables based on PASI

The following definitions will be used in this study based on the CHMP guidelines for psoriasis ([CHMP/EWP/2454/02 2004](#)):

- **PASI 75 response:** subjects achieving $\geq 75\%$ improvement (reduction) in PASI score compared to baseline are defined as PASI 75 responders
- **PASI 90 response:** subjects achieving $\geq 90\%$ improvement (reduction) in PASI score compared to baseline are defined as PASI 90 responders
- **PASI 100 response/remission:** complete clearing of psoriasis (PASI=0)

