2.2 Secondary objectives

- To evaluate the effect of secukinumab compared to placebo with respect to change from baseline in cardiometabolic biomarkers (cardiometabolic function [lipid particle size, HDL function (cholesterol efflux)], measures of inflammation [TNF-Alpha, IL-6, C-reactive protein, GlycA], adiposity [leptin and adiponectin], insulin resistance [insulin levels/glucose to yield HOMA-IR], and markers predictive of diabetes [apolipoprotein B, ferritin, IL-2 receptor A, IL-18, and fetuin-A]) at Week 12
- To evaluate the effect of secukinumab compared to placebo in subjects with moderate to severe chronic plaque-type psoriasis with respect to change from baseline in the PASI 75, 90 and 100 response rates at Week 12
- To evaluate the effect of secukinumab compared to placebo in subjects with moderate to severe chronic plaque-type psoriasis with respect to the Investigator's Global Assessment mod 2011 (IGA mod 2011) 0 or 1 response at Week 12
- To evaluate the effects of secukinumab compared to placebo with respect to change from baseline in the Dermatology Life Quality Index (DLQI) total score at Week 12
- To evaluate the clinical safety and tolerability of secukinumab as assessed by vital signs, clinical laboratory variables, and adverse event monitoring

3 Investigational plan

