5.2 Treatment groups

At Visit 2/Baseline, eligible subjects will be randomized to one of the following two treatment groups in a ratio of 1:1, with approximately 42 subjects per group:

1. **Secukinumab group:** Subjects (or trained caregivers) will self-administer (or administer to the subject) a dose of secukinumab 300 mg s.c. (two injections of the 150 mg prefilled

syringes) once weekly for five weeks (at Randomization, Weeks 1, 2, 3, and 4), followed by dosing every four weeks, starting at Week 8 through Week 48. In order to maintain the blinding during the Double-blind Induction Period, placebo s.c. doses (two injections of the placebo to 150 mg prefilled syringe) will be self-administered by the subjects (or trained caregivers) at Weeks 13, 14 and 15.

2. **Placebo group:** Subjects (or trained caregivers) will self-administer (or administer to the subject) a dose of placebo s.c. (two injections of the placebo prefilled syringes) once weekly for five weeks (at Randomization, Weeks 1, 2, 3, and 4), followed by a dose after four weeks at Week 8.

Beginning at Week 12, all subjects in the placebo group will be switched to treatment with secukinumab 300 mg s.c. Subjects will receive a dose of secukinumab 300 mg s.c. once weekly for five weeks (at Weeks 12, 13, 14, 15, and 16) followed by dosing every four weeks, starting at Week 20 through Week 48.

All subjects who enter the Double-blind Induction Period will self-administer the Week 12 dose following the completion of all assessments scheduled to be performed at Visit 8/Week 12 (Table 6-1).

The treatment groups and dosing frequency are also described in Table 5-1 below.

Table 5-1 Overview of study treatment

Treatment group	DB Treatment Period (Rand – Wk 12 pre-dose)	DB Induction Period (Wk 12 – Wk 15)	OL Treatment Period (Wk 16 – Wk 52)
Secukinumab 300 mg	2x s.c. secukinumab 150 mg injection at Rand, Wks 1, 2, 3, 4 and 8	2x s.c. secukinumab 150 mg injection at Wk 12 2x s.c. secukinumab 150 mg PBO injection at Wks 13, 14 and 15	2x s.c. secukinumab 150 mg injection at Wks 16 - 48
Placebo (PBO)	2x s.c. secukinumab 150 mg PBO injection at Rand, Wks 1, 2, 3, 4 and 8	2x s.c. secukinumab 150 mg injection at Wks 12, 13, 14, and 15	2x s.c. secukinumab 150 mg injection at Wks 16 – 48

DB = Double-blind; OL = Open-label; Rand = Randomization; Wk = Week

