Fasting labs: plasma glucose	X																					
Viral serology lab analysis: HIV, Hepatitis B and C ^G	X																					X ^d
QuantiFERON [®] TB-Gold In-Tube test ^{G,H}	X																					X ^d
Serum pregnancy test ^{G,I}	X																					X ^d
Urine pregnancy test (local) ^J		X						X													X	X ^d
FDG-PET CT ^K		X ^L						X ^M													X	
Blood sample for cardio-metabolic biomarkers ^G		X [*]				X	X	X [*]						X			X				X [*]	
PASI	X	X				X	X	X				X		X		X		X		X	X	X ^d
IGA mod 2011	X	X				X	X	X				X		X		X		X		X	X	X ^d
Alcohol use assessment			X	X	X	X	X	X				X		X		X		X		X	X	X ^d
DLQI		X						X						X		X		X		X	X	

Period	SCR	Double-blind Treatment Period							Double-blind Induction Period			Open-label Treatment Period								Unscheduled Visit ^D		
		1	2	3	4	5	6	7	8 / EOT1 _{A,B}				9	10		11		12			13	14 / EOT2 _C
Visit	1	2	3	4	5	6	7	8 / EOT1 _{A,B}				9	10		11		12		13	14 / EOT2 _C		
Week	-4 to BL ^E	BL	1	2	3	4	8	12	13	14	15	16	20	24	28	32	36	40	44	48	52	
Visit window (Days)			±2	±2	±2	±2	±2	±2				±7		±7		±7		±7		±7	±7	
Assessment																						
AE/SAE assessment ^N	X	X	X	X	X	X	X	X				X		X		X		X		X	X	X
Randomization via IRT		X																				
Subject self-administration of study treatment at site		X	X	X	X	X	X	X				X		X		X		X		X		
Dispense study treatment to subject for at-home dosing								X				X		X		X		X				
Subject self-administration of study treatment at home and completion of Self-Administration Log ^O										X	X	X		X		X		X		X		
At-home Dosing Phone Reminder ^{F,P}										X			X		X		X		X			
Check Self-Administration Log and returned used/unused study treatment and packaging ^{F,Q}												X		X		X		X		X		X ^d

AE=adverse event; BL = Baseline; DLQI=Dermatology Life Quality Index; EOT1=End of Treatment 1; EOT2=End of Treatment 2; FDG-PET CT=18-fluorodeoxyglucose positron emission tomography with computer assisted tomography; HIV=human immunodeficiency virus; IGA=Investigator's Global Assessment; IRT=Interactive Response Technology; PASI=Psoriasis Area and Severity Index; SAE=Serious Adverse Event; SCR=Screening; TB=tuberculosis

* At Visits 2, 8, and 14, subjects are required to be fasting for a minimum of 8 hours prior to the blood sample collection for cardiometabolic biomarkers

Period	SCR	Double-blind Treatment Period							Double-blind Induction Period			Open-label Treatment Period								Unscheduled Visit ^D		
		1	2	3	4	5	6	7	8 / EOT1 A,B				9		10		11		12			13
Visit	1																					

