6.5.4.3 Fasting laboratory evaluations

Fasting (8 hour duration with water *ad libitum*) laboratory tests will be performed at screening and will include:

- Plasma glucose

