9.5 Analysis of secondary variables

9.5.1 Efficacy variables

The secondary efficacy variables are the following:

- Change from baseline in each biomarker (see [Section 6.4](#))
- PASI 75 response (yes, no)
- PASI 90 response (yes, no)
- PASI 100 response (yes, no)
- IGA mod 2011 score of 0 or 1 (yes, no)
- Change from baseline in DLQI total score

Change from baseline in each biomarker and change from baseline in DLQI total score will be analyzed at each time point using the same ANCOVA model as for the primary efficacy variable, and missing data will be imputed using the LOCF method.

IGA mod 2011 score of 0 or 1 and PASI 75 / 90 / 100 responses will be analyzed at each time point using the Cochran-Mantel-Haenszel test to compare secukinumab and placebo, adjusting for body weight (<90 kg, ≥90 kg) ([Stokes, Davis, and Koch, 2012](#)). A 95% confidence interval for the difference between the two treatment groups in the proportion of subjects who are responders will be calculated using the normal approximation to the binomial distribution. For response (yes, no) at Week 12 (and other time points), a subject with a missing assessment will be considered as a responder (yes) if the subject meets the response criterion at the time of premature discontinuation from the study. Otherwise, the subject will be considered as a non-responder (no).

Analyses of the secondary efficacy variables will be based on the Full Analysis Set.

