## **2 Statistical methods**

### **2.1 Data analysis general information**

Novartis Business Services will perform the statistical analysis.

Data will be analyzed by the statistical software SAS, Version 9.4 according to Section 9 (Data Analysis) of the study protocol which will also be available in Appendix 16.1.1 of the Clinical Study Report (CSR). Important information is given in the following sections and details are provided, as applicable, which will also be in Appendix 16.1.9 of the CSR.

At the Week 12 primary analysis time point, only the independent statistician and programmer(s) from Novartis will be unblinded in order to perform the interim analysis. The same SAP will be used for interim analysis.

It is planned that the data from all centers that participate in this protocol will be combined, so that an adequate number of subjects will be available for analysis.

Unless otherwise specified, all statistical tests will be conducted against a two-sided alternative hypothesis, employing a significance level of 0.05.

Efficacy, safety, and other data will be summarized as follows:

- for continuous variables, descriptive summary statistics (number of subjects, mean, standard deviation, median, 25th and 75th percentiles, interquartile range, minimum, and maximum) at each time point and for change from baseline to each visit will be reported by treatment group.

- for categorical variables, frequency and percentage will be presented at each time point by treatment group. Percentages will be calculated with respect to the number of subjects by treatment in the analysis set of interest.

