### **2.5.2 Statistical hypothesis, model, and method of analysis**

The primary efficacy variable will be analyzed by an analysis of covariance (ANCOVA) model with treatment, baseline, and body weight (<90 kg, ≥90 kg) as explanatory variables.

Following null hypothesis ( $H_0$ ) will be tested against the alternative hypothesis ( $H_A$ ):

$$H_0: \mu_1 - \mu_0 = 0$$

$$H_A: \mu_1 - \mu_0 \neq 0$$

where  $\mu_1$  and  $\mu_0$  denote the population mean of change from baseline in the target to background ratio from the aorta at Week 12 for secukinumab group and placebo group, respectively.

The least squares means of the two treatment groups, least squares mean difference, and 95% confidence interval for the difference in the two treatment groups will be presented along with the p-value based on the fitted linear model.

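### Insulin/glucose (HOMA-IR) is analysed as change from a fasted baseline at every time point, although 4 of the 6 post-baseline biomarker draws have no required fast

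*Protocol*

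**What the plan says.** **Fasting rule.** Protocol 6.4.2 has subjects "fast for a minimum of 8 hours prior to the blood draw for the cardiometabolic biomarkers at the following visits only", and names Visit 2/Baseline, Visit 8/Week 12 and Visit 14/Week 52. The footnote to Table 6-1 agrees: "At Visits 2, 8, and 14, subjects are required to be fasting for a minimum of 8 hours". The list of markers in 6.4.2 includes insulin and glucose for HOMA-IR, with no draw schedule of their own.

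**Analysis rule.** Protocol 9.5.1: "Change from baseline in each biomarker and change from baseline in DLQI total score will be analyzed at each time point". SAP 2.7.2.1 repeats this with the primary ANCOVA model, and adds a van Elteren test if normality fails. SAP 2.12 lists insulin/glucose (HOMA-IR) among the markers analysed individually and sets no condition on fasting.

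**By-arm output.** Under SAP 2.1, descriptive statistics "at each time point and for change from baseline to each visit will be reported by treatment group". The ANCOVA in SAP 2.5.2 presents "The least squares means of the two treatment groups, least squares mean difference" and its confidence interval.

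**Objective.** Protocol 2.2 ties the biomarker comparison to a single time point; its list ends "and markers predictive of diabetes [apolipoprotein B, ferritin, IL-2 receptor A, IL-18, and fetuin-A]) at Week 12".

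**Visits and missing data.** SAP 2.4.1.1 takes biomarker data by CRF visit, but maps a discontinuation draw to the visit after the subject's last available assessment in the same period. SAP 2.7.3 imputes missing biomarker values by LOCF. SAP section 4 adds multiple imputation.

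**The concern.** The baseline subtracted in every change score is fasted, while most of the values it is subtracted from need not be. The protocol itself handles glucose as a fasting test elsewhere: section 6.5.4.3 heads the screening plasma glucose with "Fasting (8 hour duration with water", and exclusion criterion 13 uses fasting blood glucose.

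For most markers in the panel this may matter little. For insulin, glucose and an index built from them, a change from a fasted to an uncontrolled value is not a change in insulin resistance alone. At stake are the pre-specified results for this marker at Weeks 4 and 8 and at the two intermediate open-label draws. The open-label results are the most exposed. Protocol 5.2 states: "Beginning at Week 12, all subjects in the placebo group will be switched to treatment with secukinumab 300 mg s.c". From then on no untreated arm shows what the move from fasted to uncontrolled sampling does by itself.

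**Working it through.** **1. The plan's own figure.** Inputs from Protocol 9.7: difference 0.15, SD 0.196, two-sided 0.05, power 0.90. Standardised difference = 0.15/0.196 = 0.765. The noncentral t gives power 0.893 at 36 per group and 0.901 at 37, so 37 per group (74 in total) reproduces. At the quoted 0.76 SD, power is 0.897. The point below does not depend on these figures.

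**2. Count of draws (Table 6-1, biomarker row).**

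| Draw | Fast required |
|---|---|
| Baseline | yes |
| Week 4 | no |
| Week 8 | no |
| Week 12 | yes |
| Week 24 | no |
| One further open-label draw | no |
| Week 52 | yes |

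The week of the further open-label draw is uncertain in the table as read, but it carries no fasting mark, so the count stands. Post-baseline draws: 6. Without a required fast: 6 − 2 = 4. Up to Week 12: 2 of 3.

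**3. What the change score measures.** Let a share p of an arm be unfasted at a draw, and let eating shift the value by k SD.
- Expected change in an arm = drug effect + p·k.
- Between-arm contrast = difference in drug effects + (p₁ − p₀)·k. Under randomisation and blinding p₁ and p₀ should be close, so the last term is near zero.
- The SD of change grows by F = √(1 + p(1 − p)k²). This takes the shift as constant and independent of other variation.

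The by-arm change therefore carries the full p·k, while the blinded contrast mainly carries F.

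**4. Illustration (p and k are assumptions; neither document gives them).** Power is for 0.765 SD at 37 per group, against 0.901 with no inflation. The protocol does not promise this power at Weeks 4 or 8.

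| p | k (SD) | By-arm shift p·k (SD) | F | Power |
|---|---|---|---|---|
| 0.25 | 0.5 | 0.125 | 1.023 | 0.888 |
| 0.50 | 0.5 | 0.25 | 1.031 | 0.883 |
| 0.75 | 0.5 | 0.375 | 1.023 | 0.888 |
| 0.25 | 1 | 0.25 | 1.090 | 0.846 |
| 0.50 | 1 | 0.50 | 1.118 | 0.828 |
| 0.75 | 1 | 0.75 | 1.090 | 0.846 |

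With k = 0.25, power is 0.897 to 0.898, close to no loss.

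**5. Routes into Week 12.**
- *Observed Week 12 draw:* fasted.
- *Early discontinuation with an EOT1 visit:* Protocol 3.1.2 calls for the Visit 8 assessments, so this draw is fasted. The SAP 2.4.1.1 mapping can label it Week 4 or Week 8, which puts fasted and uncontrolled values under one label.
- *Neither a Week 12 nor an EOT1 sample:* LOCF carries a Week 4 or Week 8 value with no required fast.
- *Multiple imputation:* Week 4 and Week 8 values may enter the model. The SAP does not give the model.

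The intermediate open-label draws can reach Week 52 by LOCF in the same way.

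**6. Unequal carry-forward.** If m₁ and m₀ of 42 per arm are carried and each carried value is shifted by k SD, the Week 12 contrast moves by (m₁ − m₀)k/42. For 8 versus 2 and k = 1: 6/42 = 0.14 SD. For k = 0.5: 0.07 SD. Equal numbers give zero. These counts are also assumptions.

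**The case against.** The best reply is that no stated objective rests on the affected visits. The biomarker objective is at Week 12, which is fasted; the longer-term purpose in Protocol 1.2 and SAP section 1 concerns aortic inflammation; and there is no key secondary objective. That stands, and it limits the weight of the point.

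The hypothesis is also a between-arm one. SAP 5.4.1 gives the confidence interval and p-value to the treatment contrast and the arms only least squares means with standard errors. Although the SAS code would print arm intervals, no within-arm test is planned. A reader might infer that the plan makes within-arm claims; it does not. It does plan to report by-arm changes at these visits, and those cannot be interpreted as labelled.

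A reader might also infer that the Week 4 and Week 8 contrasts are biased, or that the Week 12 result fails. The documents support neither: both blinded arms follow the same draw rule, and observed Week 12 values are fasted. The opposite overstatement, that LOCF is the only way such values reach Week 12, does not hold either, because SAP section 4 also plans multiple imputation.

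Finally, the laboratory manual, which is not among the documents, may restrict this assay by visit. That cannot be ruled out. Protocol 6.4.2 describes the manual as covering sample collection, handling and shipment.

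**Conclusion.** The point holds within limits. By an explicit rule, 4 of 6 post-baseline draws have no required fast, and neither document keeps insulin/glucose (HOMA-IR) out of the change-from-baseline analysis there. This follows from the documents alone.

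- **Weeks 4 and 8:** mainly added noise in the contrast, of unknown size.
- **Intermediate open-label draws:** by-arm changes not interpretable as insulin resistance.
- **Week 12:** mainly protected. It is exposed through LOCF and possibly multiple imputation, and a shift in the contrast needs unequal carry-forward between arms.

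Every magnitude above, including the 0.14 SD example, rests on assumed inputs. The correction is worth making before lock because it is cheap and the affected results are pre-specified. It is not a threat to the stated Week 12 objective.

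**What to change.** 1. **SAP 2.7.2.1:** limit the ANCOVA and van Elteren analyses of insulin, glucose and HOMA-IR to Week 12 and Week 52. List or summarise the other draws descriptively, marked 'no required fast'.
2. **SAP 2.7.3:** keep the visit mapping and the planned Week 12 LOCF and multiple imputation analyses. Add one sensitivity analysis for this marker in which only required-fast draws, identified by CRF visit, are used, carried forward or entered in the imputation model. An early fasted EOT1 or EOT2 draw counts as the last fasted value for Week 12 or Week 52 of its period.
3. **SAP section 4:** record the departure from the protocol's analysis at every time point.

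If the laboratory manual already limits this assay to fasted visits, state that in SAP 2.12 instead. The other biomarkers stay as planned.

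**Cost:** SAP wording and one sensitivity table; no change to visits or samples. This marker loses its inferential results at the four draws without a required fast. The sensitivity analysis can omit subjects with no fasted post-baseline draw, which may introduce selection, so it supplements the planned analyses and does not replace them.
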